10.8 Intervention Discontinuation and Participant Discontinuation/Withdrawal

In consenting to the trial, participants agree to all trial activities including administration of trial intervention and treatment and follow-up assessments / visits and data collection. Every effort should be made to facilitate the completion of these for every recruited participant. If it is not possible to complete these activities (or it is deemed inappropriate) the reasons why should be documented. The following sub-sections describe the different levels of discontinuation/withdrawal.

Premature Discontinuation of Study Intervention

Participants may discontinue treatment for reasons including, but not limited to:

- Participant-led i.e. request by the participant / legal representative
- Unacceptable toxicity (see Section 11 for Adverse Event reporting)
- Intercurrent illness preventing further treatment.
- Clinician-led:
 - Any change in the participant's condition that justifies the discontinuation of treatment in the clinician's opinion.
 - Reasons of non-adherence or non-compliance with treatment or other trial procedures
 - Participant develops renal failure that is a contraindication to levetiracetam

Discontinuation from study intervention does not mean discontinuation of the study altogether, and the remaining study procedures, follow up assessment / visits and data collection should be completed as indicated in the protocol (unless consent is specifically withdrawn) prior to unblinding.

Participant Withdrawal from Follow Up

Participants are free to withdraw from follow up at any time without providing a reason, though a reason should be recorded if one is given. Those who wish to withdraw from further follow-up will have the data collected up to the point of that withdrawal included in the analyses. The participant will not contribute further data to the study and the LCTC should be informed via email to the LCTC and via completion of a Withdrawal CRF to be returned to the LCTC within 7 days.

If participants express a wish to withdraw from follow up, the research team at site should ascertain if this is for all elements of trial follow-up, or if for example data from routine assessments can still be collected for the trial. In the case of ongoing adverse events, participants should be given appropriate care under medical supervision until the symptoms of any adverse event resolve or the patient's condition becomes stable. Any SARs will be notifiable to the LCTC via processes detailed in Section 12 even if a participant has withdrawn from follow up.

Participant Transfer

If a participant moves from the area, every effort should be made for the participant to be followed-up at another participating trial centre and for this trial centre to take over responsibility for the participant or for follow-up via GP.

For all transfers, a transfer case report form (CRF) will be completed by the current site and returned to LCTC. LCTC will then forward the transfer CRF on to the new site; the PI at the new site will be asked to sign this CRF and return to LCTC to confirm that they are taking over responsibility for the participant in the trial.

The current centre should provide a copy of the participant's full CRF to the new site. The participants remains the responsibility of the original site until the new site PI has signed the transfer CRF.

If participant transfer to another participating centre is not possible then the participant would be considered as lost to follow-up.

Loss to Follow-up

A participant will be considered lost to follow up if s/he fails to return for scheduled visits and is not contactable by the site research team.

If a participant fails to attend/facilitate a required study visit the following action must be taken:

- Sites should attempt to contact the participant and reschedule the missed visit within the given windows and advise the participant on the importance of maintaining the assigned visit schedule.

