- The participant will be asked to confirm treatment compliance, willingness to continue and be advised about the next visit.

Checks on suicidal ideation and psychosis should be made and managed clinically as per routine practice.

In patients who develop seizures after completing the 14-day course of trial treatment, any investigations/treatment will be coordinated as per usual NHS practice. Participants will not be unblinded as the study treatment has stopped and the participant will remain on study and continue follow-up for 12 months. Information about the commencement of AED will be collected.

Follow-up 2: 12 weeks (±4 weeks) post-surgery (clinic visit – face-to-face or video consultation)

This will be conducted where possible during a scheduled hospital appointment where the participants progress will be evaluated and the following information collected:

- Details of any AEDs prescribed.
- Symptoms of possible seizures reviewed.
- Performance status assessed using Karnofsky Performance Status [KPS] scale.
- Quality of life using EQ-5D-5L questionnaire (participant completed or interviewer).
- Resource Use Questionnaire will be completed and collected (participant completed or research team, if remote).
- 30-day morbidity and mortality will be collected using Landriel Ibañez classification system (*if not already collected at Follow-up visit 1*).
- The participant will be asked to confirm treatment compliance (if not confirmed at follow-up 1) confirm willingness to continue and advised about the next visit.

Checks on suicidal ideation and psychosis should be made and managed clinically as per routine practice.

Follow-up 3: 24 weeks (±4 weeks) post-surgery (telephone consultation)

This is a scheduled telephone visit and will be a discussion between the participant and a staff member.

- Details of any Anti-Epileptic Drug (AED) prescribed.
- Staff will collect details of any potential seizure symptoms.
- The participant will be asked to confirm willingness to continue and be advised about the next visit.

Follow-up 4: 36 weeks (±4 weeks) post-surgery (telephone consultation)

This is a scheduled telephone visit and will be a discussion between the participant and a staff member.

- Details of any Anti-Epileptic Drug (AED) prescribed.
- Staff will collect details of any potential seizure symptoms.
- The participant will be asked to confirm willingness to continue and be advised about the next visit.

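### Section 10.8 classes a participant who moves and cannot be transferred as lost to follow-up even if still contactable, which is inconsistent with the protocol's other follow-up provisions

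*Protocol*

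**What the plan says.** Section 10.8 opens its discussion of discontinuation with a general duty towards all trial activities, follow-up included: "Every effort should be made to facilitate the completion of these for every recruited participant".

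Under Participant Transfer, the same section asks that someone who moves away be followed at another participating centre, which would "take over responsibility for the participant or for follow-up via GP". It then sets out the transfer form and says that the participant "remains the responsibility of the original site until the new site PI has signed the transfer CRF". The sub-section ends: "If participant transfer to another participating centre is not possible then the participant would be considered as lost to follow-up".

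The next sub-section, Loss to Follow-up, describes a lost participant as one who "fails to return for scheduled visits and is not contactable by the site research team". It tells sites to try to contact the participant and rebook a missed visit.

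Section 10.7 fixes the visit modes. Follow-ups 1, 2 and 5 are clinic visits, held face to face or by video. Follow-ups 3 and 4 are by telephone. For each of these two the protocol says: "This is a scheduled telephone visit and will be a discussion between the participant and a staff member". Possible seizure symptoms are collected at all five.

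**The concern.** The closing transfer sentence turns on one fact only: whether another participating centre can take the participant. A person who has moved, answers the telephone and is willing to carry on would be recorded as lost. A site that reads this has no instruction to keep calling, and sites may read it differently.

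What is at stake is the primary outcome. Section 9 defines it as at least one seizure at 12 months, a yes/no status. A participant who is seizure-free when follow-up stops early has no 12-month status. Section 6 relies on intention-to-treat analysis to limit attrition bias, but that principle cannot supply outcomes that were not collected. The sample size allows for 5% dropout (section 13.2). Withdrawal/attrition is also a stop/go indicator in the internal pilot (section 6.4: green at or below 5%, red at or above 10%), so two different notions of loss could affect how that indicator is counted.

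**Working it through.** **1. The provisions side by side, for a participant who has moved, has no receiving centre and can be reached**

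| Provision (section 10.8) | Status or duty it implies |
|---|---|
| Participant Transfer, last sentence | Lost to follow-up |
| Participant Transfer, GP clause | Follow-up can continue through the GP |
| Participant Transfer, responsibility clause | No new investigator signs, so the original site stays responsible |
| Opening paragraph | Effort to complete follow-up continues |
| Loss to Follow-up | Not lost on this description, because one of its two joined conditions (not contactable) fails |

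The first row is out of line with the other four. The clash with the GP clause is the most direct, since both stand in one sub-section and the last sentence ignores the alternative already offered.

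**2. Could the outcome still be obtained?** Follow-ups 3 and 4 are by telephone, and 1, 2 and 5 may be by video (section 10.7). The seizure definition in section 21.1 is based on symptoms. Participants hold a symptom checklist and the site team's contact details (section 10.7, Process for Monitoring Seizures). Symptom reports can therefore reach the original site by modes already in the schedule. Two items may need local attendance: the 12-month MRI, and neurology input where it is needed to confirm a diagnosis.

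**3. The plan's own sample size.** Inputs from section 13.2: proportions 0.12 and 0.06, two-sided 5%, power 90%, 5% dropout.

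- n per group = [1.960 × √(2 × 0.09 × 0.91) + 1.282 × √(0.12 × 0.88 + 0.06 × 0.94)]² / 0.06²
- = [0.7932 + 0.5158]² / 0.0036 = 476.01, rounded up to 477. This agrees with the protocol.
- Power at 477 per group: 0.9006.
- Total: 2 × 477 / 0.95 = 1004.2, stated as 1004. This agrees to the nearest whole number.

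**4. Size of the effect.** The documents give no rate of moving, so the total loss is an assumed range. With 1004 randomised:

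| Total loss | Evaluable | Power |
|---|---|---|
| 5% (plan) | 954 | 90.05% |
| 6% | 944 | 89.75% |
| 7% | 934 | 89.44% |
| 8% | 924 | 89.12% |
| 10% | 904 | 88.45% |

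In events: the plan expects 477 × (0.12 + 0.06) = 85.9, about 86. If, purely for illustration, 1–2% of 1004 (10–20 people) were affected, at the average rate of 9% they would carry 0.9–1.8 expected events. Some of those would occur before the move and would already count.

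**The case against.** The case for leaving the text alone has several parts.

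- **The sentence assigns a label and does not order sites to stop.** This stands. A reader might infer that obtainable data are thrown away by design. The documents do not support that: nothing forbids further contact or GP data, and the surrounding clauses favour continuing. What remains is a risk that sites act on the label.
- **The Loss to Follow-up text says if, not only if.** This stands in part. A reader might infer a flat contradiction of a definition, but the two sentences can be read as separate routes to one status. The tension with the GP clause, the responsibility clause and the general duty does not depend on that reading.
- **Few people will be affected.** This stands. The pilot's green threshold is at least 20 open sites, so someone who moves within the UK or Ireland will often have a participating centre available. A reader might infer 10–20 discarded outcomes, but that rests on an assumed 1–2% with no basis in the documents. Part of the 5% allowance may also be meant for relocations.
- **No bias between arms is shown.** This stands. People who move may differ in prognosis, but bias in the comparison needs more than that, such as loss related to both arm and outcome. Treatment is blinded and lasts 14 days, and no mechanism is evident. Section 13.6 leaves missing-data methods to the SAP.
- **Remote follow-up may be incomplete.** This stands for the MRI and for neurology confirmation. It does not stand for symptom reports, on which the primary outcome mainly depends.

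The SAP cannot settle the matter: this is an instruction to sites, and an analysis plan can only deal with the gaps that it leaves.

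**Conclusion.** The inconsistency is real and can be checked within section 10.8. Followed literally, the last transfer sentence can create missing 12-month seizure outcomes that the existing schedule could avoid. That conclusion assumes that some sites would treat the label as a reason to stop contact, which the text permits but does not require.

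The size is modest. The number affected is not given and is probably small. Even 1–2 percentage points of extra loss would cost less than one percentage point of power (from 90.05% to 89.75–89.44%). The case for change is a consistent rule and avoidable missing primary outcomes at almost no cost. It is not a loss of power, and it is not a demonstrated bias.

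**What to change.** Replace the last sentence of Participant Transfer in section 10.8 with:

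*If transfer is not possible, the original site continues follow-up by telephone or video and/or via the GP; the participant is classed as lost to follow-up only if not contactable after the attempts described below.*

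This brings the sub-section into line with its GP clause, its responsibility clause, the general duty at the head of section 10.8 and the Loss to Follow-up text. It needs no new visit or procedure.

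The cost is slight extra remote work for the original site. The 12-month MRI and any neurology confirmation may have to be arranged locally or be missing. Section 10.7 lists follow-ups 1, 2 and 5 as face to face or video, so if a telephone call is to be accepted for them when video is not feasible, that section should say so.

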10.9 End of Trial

The end of the trial is defined to be the date on which data for all participants is locked and data entry privileges are withdrawn from the trial database.

Individual sites may be closed to recruitment prior to their intended recruitment end date if the TMG have concerns about their capacity or capability to deliver the trial, or for operational reasons whereby resources are better used at sites with better capacity to recruit.

Site and closure activities will be centrally coordinated and conducted in accordance with LCTC processes regardless of whether the trial closes as planned or prematurely. This includes activities such as:

- End of Trial notification to REC and competent authority e.g. MHRA.
- Trial-related materials reconciled and returned/disposed of as appropriate
- All site data entered onto the study database, discrepancies raised and satisfactory responses received
- Quality Control checks of the Investigator Site Files, Pharmacy Site Files and Trial Master File as appropriate.

11 SUB-STUDIES/NESTED STUDIES

STOP'EM will yield a valuable repository of blood samples and MRI scans. The planned analyses/sub-studies will not be part of STOP'EM itself and is not funded by NIHR as part of NIHR129748, but will form part a separate 'study within a trial' application for a PhD research fellowship.

Sub-study 1 (inflammatory biomarkers) [optional for sites]

Two participating study sites (Liverpool and Cambridge) will consent participants to donate blood samples which will be used for future studies to identify inflammatory biomarkers. Blood samples will be taken at 5 time-points:

- knife-to-skin
- 1 hour after knife-to-skin
- 4 hours after knife-to-skin
- 24 hours after knife-to-skin
- 48 hours after knife-to-skin

Samples will be centrifuged; red cells and supernatant will be stored in aliquots at -70°C. A separate sample preparation document will be provided which describes the process in more detail. Samples collected in any participating sites will be held within the Cambridge Neurosurgical Laboratories, [name]. Blood samples will be stored until they are used for translational research.

Other sites can also participate in the translational research element of STOP'EM, if they wish to and have capacity/funds available to collect and store samples.

Samples are being gifted as part of future research which may include genetic testing for specific biomarkers of inflammation that could have an effect on seizure risk. Separate funding and regulatory approvals will be sought for this future research.

Sub-study 2 (imaging biomarkers) [mandatory for all sites]

All participants will undergo an MRI at baseline (pre-operatively) and at ~52 weeks post-operatively, as part of their routine care and follow-up. Images will be pseudo-anonymised and transferred electronically, via the Image Exchange Portal, for central review.

A separate MRI manual will be provided to sites – this will contain imaging sequences and transfer instructions.

The storage of MRIs is not part of the STOP'EM study and is not funded by NIHR as part of NIHR129748.

12 SAFETY REPORTING

Safety reporting in clinical trials is a legal and ethical requirement and it is imperative that all applicable requirements detailed here are followed during the trial. For STOP'EM, data on Serious Adverse Reactions and Suspected Unexpected Serious Adverse Reactions will be collected

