5.3 Risk and Benefits

Potential Risks

This trial is categorised as Type B (Somewhat higher than the risk of standard medical care) as per the risk-adapted approach to clinical trials adopted by the MHRA.

The potential toxicity associated with a 14-day course of levetiracetam is small, but side effects can occur and these will be recorded as part of the study and the frequency and severity monitored by the IDSMC. Most side effects occur with longer-term use and we therefore do not anticipate a high reporting rate in STOP'EM.

More detail regarding management of risks associated with this trial are detailed in a separate Risk Assessment maintained in the Trial Master File.

Potential Benefits

For the participant: The potential benefit of seizure prophylaxis in meningioma surgery must be balanced against the risks^[4, 5, 13, 17]. There have not been any randomized placebo-controlled trials of prophylactic AEDs in seizure-naive patients with meningioma^[18].

The current evidence for seizure prophylaxis in meningioma surgery is limited and there is ongoing uncertainty as to whether it is of benefit^[3, 12, 16, 17, 19-23]. However, a recently published (2018) meta-analysis of 352 brain tumour patients from randomized controlled trials, treated using phenytoin as prophylaxis, showed a reduction in acute symptomatic seizure risk within the first week of surgery (RR = 0.352, 95% confidence interval 0.130–0.949, $p = 0.039$), but no benefit at reducing the proportion with epilepsy at 12 months (RR 1.033, 95% CI 0.498–2.141, $p = 0.931$)^[24]. Whilst this study shows potential benefit, it has limitations: the analysis included only 97 patients with meningioma and adverse events were poorly reported but affected 32% of patients.

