5.4 Objectives

Primary objectives	1. To determine whether 2 weeks prophylactic levetiracetam treatment reduces the risk of developing seizures within 12 months of surgical resection of newly-diagnosed seizure naïve meningioma compared to placebo
Secondary objectives:	2. To improve the understanding of the safety of prophylactic levetiracetam 3. To determine whether prophylactic levetiracetam influences quality of life 4. To determine the 30-day morbidity and mortality associated with meningioma surgery
Economic objective:	5. To estimate the cost effectiveness of prophylactic levetiracetam in seizure-naïve meningioma
Exploratory/ Translational objective:	6. To create a repository of MRI scans and blood samples for future research, investigating imaging and blood biomarkers that may predict seizure development

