9 OUTCOMES

Outcomes:		Corresponding objective:
Primary outcome:	1. At least one seizure at 12 months post-surgery	1
	2. Time to first seizure	1
Secondary Outcomes:	3. Time to first convulsive seizure	1
	4. Time to first unprovoked seizure (seizure from day 8 onwards)	1
	5. Driving under licence by 12 months	1;3
	6. EQ-5D-5L	3
	7. Serious adverse reactions	2
	8. Landriel Ibañez classification	4
Economic outcomes:	9. Incremental cost per quality-adjusted life year (QALY) gained	5
	10. 12-month resource use associated with NHS and personal social services	5

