Grade IIa	Complication requiring intervention without general anaesthesia 
 • Dehiscent non-infected wound requiring closure under local anaesthesia • Subgaleal CSF collection (pseudomeningocele) requiring lumbar drain

Grade IIb	Complication requiring intervention with general anaesthesia 
 • CSF leak requiring surgical repair • Wound infection requiring surgical lavage / bone flap removal • Pseudomeningocele requiring external ventricular drain or shunt
Grade III	Life-threatening complication that may require management in critical care
Grade IIIa	Complication involving single organ failure 
 • Acute hydrocephalus requiring external ventricular drain or shunt • Intracranial haematoma requiring re-operation • Cerebral oedema requiring intubation
Grade IIIb	Complication involving multiple organ failure 
 • Meningitis and pneumonia (or other organ failure e.g. renal) • Intracranial hypertension and haemodynamic instability • Ischaemic stroke and pneumonia (or other organ failure e.g. renal)
Grade IV	Complication resulting in death

Process for Monitoring Seizures

Patients will be given contact details for the site research team, as well as a checklist of symptoms to look out for that might be seizures. If a patient develops any of these symptoms, they will contact the research team. The patient will be assessed by the research team to see if the symptoms are consistent with seizures.

As per routine clinical pathways, local neurology input may be required to confirm the diagnosis and commence appropriate anticonvulsant medication.

MRI scans

MRI will be performed in all participants as per routine clinical practice at baseline (pre-operatively) and 12 months. Details of imaging sequences are given in the separate MRI manual, alongside instructions on how to transfer pseudoanonymised images to The Walton Centre.

Efficacy Assessments

Details of signs and symptoms of possible seizures, and of any AED prescribed will be collected at every follow-up time point.

Safety Assessments

All participants will complete a symptoms checklist, administered by a research nurse, 4-6 weeks post-surgery (follow-up 1). This will help determine any adverse reactions specifically related to the IMP.

Quality of Life Assessments

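### Serious adverse reactions are the only outcome tied to the safety objective, so non-serious tolerability has no defined comparison between arms, and the protocol disagrees with itself on whether such reactions are recorded

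*Protocol*

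**What the plan says.** Objective 2 (section 5.4) is "To improve the understanding of the safety of prophylactic levetiracetam". In the outcome tables (sections 3 and 9) the only outcome carrying that objective is "Serious adverse reactions". Section 12 opens by saying that "data on Serious Adverse Reactions and Suspected Unexpected Serious Adverse Reactions will be collected". The schedule of assessments and the follow-up 1 list in section 10.7 also name serious adverse reactions as the only adverse-reaction item.

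Other sections reach further. Section 5.3 says of a 14-day course that "side effects can occur and these will be recorded as part of the study and the frequency and severity monitored by the IDSMC". Section 10.7, under Safety Assessments, has all participants complete a nurse-administered symptoms checklist at 4-6 weeks and gives its purpose: "This will help determine any adverse reactions specifically related to the IMP". Section 12.3 asks for a severity grade on every adverse reaction, serious or not. Section 12.6 lists events that have to be recorded, and the list is limited neither to serious nor to related events.

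**The concern.** To count towards the safety outcome, an event must meet the seriousness criteria of section 12.2 and be judged at least possibly related under section 12.4. The side effects named for levetiracetam in section 5.2, such as mood disturbance, somnolence, fatigue and balance disturbance, will seldom be serious. After a craniotomy they also have a ready alternative explanation, and the section 12.4 definition of an unlikely relationship cites the participant's clinical condition as an example of one. A placebo-controlled, double-blind comparison does not need individual attribution to show an excess of a symptom, so filtering on attribution gives up sensitivity.

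Two things are at stake. First, a site reading sections 5.3, 10.7, 12, 12.3 and 12.6 cannot tell whether a non-serious reaction is to be recorded. If section 12 governs, the IDSMC cannot do what section 5.3 says it will do. Second, if the trial favours prophylaxis, the planned safety outcome will say little about the tolerability of the 14-day course, although the data that could address it are to be collected from everyone.

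**Working it through.** **1. The sections side by side (Protocol).**

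| Section | What is recorded or analysed |
|---|---|
| 3 and 9, outcome tables | Serious adverse reactions, the only outcome for objective 2 |
| 10.7, schedule and follow-up 1 list | Serious adverse reactions; the safety checklist is not listed |
| 12, opening | SARs and SUSARs |
| 5.3 | Side effects, with frequency and severity going to the IDSMC |
| 10.7, Safety Assessments | Symptoms checklist in all participants |
| 12.3 | Severity of all adverse reactions |
| 12.6 | Broad list, not limited to serious or related events |

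The first three rows are narrow and the last four are wide. The schedule row on symptoms of possible seizures is an efficacy item and does not stand in for the safety checklist. The section 12.9 flowchart could not be read and is not relied on here.

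**2. Timing of the checklist.** Section 8.4 makes day 1 the day before surgery and day 2 the day of surgery, so day 14 is post-operative day 12. Follow-up 1 is at 4-6 weeks, post-operative days 28 to 42. The gap after the last dose is 28 − 12 = 16 days to 42 − 12 = 30 days.

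**3. The plan's own figure.** With no continuity correction,

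power = Φ{ [ |p1 − p0|√n − 1.96√(2p̄(1 − p̄)) ] / √(p0(1 − p0) + p1(1 − p1)) }.

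Section 13.2 has 0.12 v 0.06 and n = 477 per group: (1.3104 − 1.96 × 0.4047) / 0.4025 = 1.285, so power is 90.06%. Dropout: 954 / 0.95 = 1004.2, matching 1004. The plan's sample size reproduces and is not in dispute. It gives 1004 / 2 = 502 randomised and 477 evaluable per arm.

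**4. Serious adverse reactions, 502 per arm.** The protocol gives no rates, so all those below are assumptions. Counts are too small for the normal approximation, so power is the sum of the binomial probabilities of all tables for which Fisher's exact test gives p ≤ 0.05.

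| Assumed rates | Expected events | Fisher power | Normal approximation |
|---|---|---|---|
| 0.2% v 0.6% | 1.0 v 3.0 | 4% | 17% |
| 0.5% v 1.0% | 2.5 v 5.0 | 7% | 15% |
| 0.5% v 1.5% | 2.5 v 7.5 | 24% | 36% |
| 1.0% v 2.0% | 5.0 v 10.0 | 18% | 26% |
| 1.0% v 3.0% | 5.0 v 15.1 | 56% | 62% |

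The approximation is shown only because it flatters the outcome; the Fisher column is the one to use.

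**5. One checklist symptom, 477 per arm.** Rates are again assumed, with the formula of step 3.

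- 15% v 18%: (0.6552 − 1.96 × 0.5249) / 0.5245 = −0.712, power 24%.
- 15% v 20%: (1.0920 − 1.96 × 0.5374) / 0.5362 = 0.072, power 53%.
- 15% v 22%: (1.5288 − 1.96 × 0.5491) / 0.5469 = 0.827, power 80%.
- Other baselines: 5% v 10%, 84%; 10% v 15%, 65%.

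These are for a single symptom at the 5% level, with no allowance for examining several.

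**The case against.** The strongest reply is that the objective is modest and the plan is not empty. Objective 2 asks only for better understanding, with no hypothesis. Site staff are blinded (section 6.2) and causality is assessed without unblinding (section 12.11), so attribution should be largely even between arms. Serious adverse reactions can be compared, and none among 502 would bound the rate below 1 − 0.05^(1/502) = 0.6% (one-sided 95%). Deaths are notified whatever their cause (section 12.8), and Landriel Ibañez grades, KPS and EQ-5D-5L are collected in both arms. Section 5.3 expects little toxicity from a short course. How a collected checklist is tabulated may properly be left to the SAP.

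Much of that stands. A reader might infer that the safety objective cannot be answered, or that attribution throws away the protection of the placebo arm. The documents support neither: attribution costs sensitivity, but the arms remain comparable. A reader might also infer that section 5.2 names these side effects as the harms that matter in this trial. That passage is about long-term use, so it cannot be carried over to 14 days without saying so. Nor is it settled that recording is confined to serious reactions, because sections 12.3 and 12.6 point the other way.

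What the reply does not remove is that section 9 itself assigns one outcome to objective 2, and choosing outcomes is a protocol matter. Landriel Ibañez grading covers surgical complications and serves objective 4. The first post-operative EQ-5D-5L and KPS come after treatment has ended. None of these is a defined comparison of non-serious tolerability during the course.

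**Conclusion.** The point holds as an inconsistency in what is recorded, together with a gap in the outcomes. Objective 2 rests on one outcome that is rare and filtered by attribution. The protocol also contradicts itself on whether non-serious reactions are recorded, and the checklist meant to detect them is absent from both the schedule and the outcome list.

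On size, under assumed rates of 0.2-1% v 0.6-3%, the power to see a difference in serious adverse reactions runs from about 4% to 56%. For a single checklist symptom it runs from about 24% (15% v 18%) to 84% (5% v 10%). The checklist is thus no guarantee of detecting a small excess, but it would describe non-serious harms that the planned outcome cannot. All these figures depend on assumed rates. The SAP and the checklist wording are not shown, so whether the form asks about the treatment period is something to check, not an established fault. The primary analysis is unaffected.

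**What to change.** - **Section 9, objective 2:** add the proportion of participants reporting each checklist symptom, and any symptom, during the treatment period, by arm and irrespective of judged causality. Differences with 95% confidence intervals would suffice; with several symptoms, single p-values should not be over-read.
- **Section 10.7:** add the checklist to the schedule and the follow-up 1 list. Check that its wording covers the 14 treatment days, given the gap of 16-30 days since the last dose.
- **IDSMC closed reports:** include the table, so that the statement in section 5.3 is true.
- **Sections 5.3, 10.7, 12, 12.3 and 12.6:** reconcile them so that sites know which non-serious events are recorded.
- Keep serious adverse reactions as an outcome and for expedited reporting.

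The cost is wording in the protocol, SAP and possibly the checklist; there is no new visit or procedure. The downside is reliance on recall. That should be similar in both arms except among the few participants unblinded after an early seizure (section 8.5 puts seizures in the first two weeks at about 2-3%).
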